## Statistical Analysis Plan

### REVISION HISTORY

Version	Version Date	Author	Summary of Changes Made
Draft 0.1	07/Dec/2015		New Document
Draft 0.2	03/Feb/2016		Implementation of sponsor comments
Draft 0.3	24/Feb/2016		Incorporated sponsor comments plus refinements.
Draft 0.4	17/Mar/2016		Incorporated sponsor comments and display of protocol deviations and screening failures
Draft 0.5	15/Apr/2016		Incorporated sponsor comments
Draft 0.6	09/May/2018		Updates for Protocol Amendment 4.0 (dated 31/Jan/2018) and sponsor comments
Draft 0.7	29/May/2018		Implementation of sponsor comments
Draft 0.8	27/Jun/2018		Implementation of sponsor comments
Draft 0.9	13/Jul/2018		Implementation of sponsor comments
Final 1.0	18/Jul/2018		Comments resolution

Chiesi

CCD-5633AA1-02

Final 1.0

18/July/2018

TP-EP.BS-WW-001-05

Effective date: 29 Jul 15

Related to: SOP-EP.BS-WW-002

Page 2 of 46

## Statistical Analysis Plan

### LIST OF IN-TEXT TABLES / FIGURES

Not applicable.

Chiesi

Final 1.0

CCD-5633AA1-02

18/July/2018

---

TP-EP.BS-WW-001-05

Effective date: 29 Jul 15

Related to: SOP-EP.BS-WW-002

Page 5 of 46

## Statistical Analysis Plan

### ABBREVIATION AND ACRONYM LIST

Abbreviation / Acronym	Definition / Expansion
ADR	Adverse drug reactions
AE	Adverse event
ALT	alanine aminotransferase
AOP	Apnea of prematurity
AST	aspartate aminotransferase
ATC	Anatomical therapeutic chemical
BiPAP	Bi-level positive airway pressure
BPD	Bronchopulmonary dysplasia
bpm	Beats per minute
CI	Confidence interval
CMH	Cochran-Mantel-Haenszel
CPAP	Continuous Positive Airway Pressure
CS	Clinically significant or Cranial Sonography
CSP	Clinical Study Protocol
CX	Chest X-Ray
DBP	Diastolic blood pressure
eCRF	Electronic Case Report Form
FBC	Full blood count
FiO 2	Fraction of inspired oxygen
GA	Gestational age
GMH	Germinal matrix
H	High (value above upper limit of reference range)
HFNC	High flow nasal cannula
HFOV	High Frequency Oscillatory Ventilation
HL	Hodges-Lehmann
HR	Heart rate
IL1 $\beta$	Interleukin 1 $\beta$

Chiesi

Final 1.0

CCD-5633AA1-02

18/July/2018

TP-EP.BS-WW-001-05

Effective date: 29 Jul 15

Related to: SOP-EP.BS-WW-002

Page 6 of 46

## Statistical Analysis Plan

Abbreviation / Acronym	Definition / Expansion
IL6	Interleukin 6
IMV	Intermittent Mandatory Ventilation
IRT	Interactive Response Technology
ITT	Intention to treat (population)
IVH	Intraventricular hemorrhage
IVRS	Interactive Voice Response Services
IWRS	Interactive Web Response System
L	Low (value below lower limit of reference range)
MAP	Mean airway pressure
MedDRA	Medical Dictionary for Regulatory Activities
MMRM	Mixed model for repeated measures
MOP	Myeloperoxidase
NC	Neonatal Complications of prematurity
NCS	Not clinically significant
NEC	Necrotizing enterocolitis
NHFV	Nasal High frequency ventilation
nIMV	Nasal Intermittent Mandatory Ventilation
NIPPV	Nasal intermittent positive pressure ventilation
NK	Not known
NPSV	Nasal Pressure Support Ventilation
nSIMV	Nasal Synchronized Intermittent Mandatory Ventilation
nSIPPV	Nasal Synchronized Intermittent Positive Pressure Ventilation
OI	Oxygenation index
OR	Odds ratio
OSI	Oxygen saturation index
PaO 2	Partial pressure of oxygen in arterial blood
PDA	Patent ductus arteriosus
PEEP	Positive end-expiratory pressure
PH	Pregnancy history

Chiesi

Final 1.0

CCD-5633AA1-02

18/July/2018

## Statistical Analysis Plan

Abbreviation / Acronym	Definition / Expansion
PIE	Pulmonary interstitial emphysema
PIP	Peak inspiratory pressure
PK	Pharmacokinetic
PMA	post menstrual age
PNA	post-natal age
POC	Proof of Concept
PP	Per protocol
PT	Preferred term
PTV	Patient trigger ventilation
PVL	Periventricular leukomalacia
RDS	Respiratory Distress Syndrome
ROP	Retinopathy of prematurity
RR	Relative risk
RSS	Respiratory severity score
SAE	Serious adverse event
SAF	Safety Population
SAP	Statistical Analysis Plan
SBP	Systolic blood pressure
SD	Standard deviation or single dose
SE	Standard error
SIMV	Synchronized intermittent mandatory ventilation
SIPPV	Synchronized intermittent positive pressure ventilation
SOC	System Organ Class
SpO 2	Arterial oxygen saturation
TEAE	Treatment-emergent adverse event
TLF	Tables, Listings and Figures
TNF- $\alpha$	Tumor Necrosis Factor-alpha
VS	Ventilatory Support
WHO-DD	World Health Organization - Drug Dictionary
Y/N	Yes/No

Chiesi

Final 1.0

CCD-5633AA1-02

18/July/2018

## Statistical Analysis Plan

### STATISTICAL ANALYSIS PLAN

The Statistical Analysis Plan (SAP) details the statistical methodology to be used in analyzing study data and outlines the statistical programming specifications for the Tables, Listings and Figures (TLFs). It describes the variables and populations, anticipated data transformations and manipulations and other details of the analyses not provided in the Clinical Study Protocol (CSP).

The analyses described are based on the final amended CSP Version 4.0, dated, 31/Jan/2018.

The SAP will be finalized prior to database lock and describes the statistical analysis as it is foreseen when the study is being planned. If circumstances should arise during the study rendering this analysis inappropriate, or if improved methods of analysis should arise, updates to the analyses may be made. Any deviations from the SAP after database lock, reasons for such deviations and all alternative or additional statistical analyses that may be performed, will be described in a SAP Addendum.

The 24-months assessment analysis will be described in a separate SAP.

### 1. STUDY OBJECTIVES

This trial is a multicenter, double-blind, randomized, single dose, active-controlled, Proof of Concept (POC)/Phase II study to investigate the efficacy and safety of synthetic surfactant (CHF 5633) in comparison to porcine surfactant (Poractant alfa, Curosurf®) in the treatment of preterm neonates with Respiratory Distress Syndrome (RDS).

#### 1.1 Primary Objectives

Main objectives of this study are:

- to investigate the short term efficacy profile of CHF 5633 vs. porcine surfactant (Poractant Alfa, Curosurf®) in terms of reduced oxygen requirement and ventilatory support (VS)
- to evaluate the mid-term efficacy profile in terms of reduced incidence of bronchopulmonary dysplasia (BPD) and mortality/BPD rate at 36 weeks post menstrual age (PMA), mortality rate at 28 days post-natal age (PNA) and 36 weeks PMA, RDS-associated mortality through 14 days of age and other major co-morbidities of prematurity.

#### 1.2 Secondary Objectives

Other objectives of the present study are:

Chiesi

Final 1.0

CCD-5633AA1-02

18/July/2018

## Statistical Analysis Plan

- to evaluate the need for re-dosing in the two treatment groups according the pre-defined criteria;
- to evaluate the inflammatory status through the measurements of specific biomarkers of inflammation in tracheal aspirates (in a subgroup of babies who require endotracheal intubation for mechanical ventilation when feasible);
- to assess immunogenicity through the measurement of antibodies to SP-B analogue (CHF 5736.03) and SP-C analogue (CHF 4902.03) contained in CHF 5633;
- to perform the evaluation of oxygenation status through invasive measurements [in a subgroup of babies who have an arterial (umbilical, peripheral) access, when feasible];
- to evaluate the safety profile in the two treatment groups in terms of adverse events (AEs) and adverse drug reactions (ADRs), vital signs, hematology and biochemistry values.

## 2. STUDY DESIGN

The Schedule of Assessments is presented in Appendix 1.

## 3. STUDY POPULATION

A total number of 126 (63 in each treatment group) preterm neonates with a gestational age of 24+0 weeks up to 29+6 weeks with RDS, will be randomized in the study. Detailed lists of inclusion and exclusion criteria are shown in Sections 4.2 and 4.3 of the CSP.

## 4. STATISTICAL BASIS FOR SAMPLE SIZE

According to the exploratory nature of this study, no formal sample size calculation was performed. A maximum number of sixty-three randomized neonates per treatment group (126 in total) is deemed sufficient to describe the efficacy and safety of CHF5633 compared to Poractant Alfa.

Chiesi

Final 1.0

CCD-5633AA1-02

18/July/2018

---

TP-EP.BS-WW-001-05

Effective date: 29 Jul 15

Related to: SOP-EP.BS-WW-002

Page 10 of 46

## Statistical Analysis Plan

### 5. RANDOMIZATION

A dynamic randomization method was used to balance the treatment groups by investigational site and gestational age group (i.e. from  $24^{+0}$  to  $26^{+6}$  weeks and from  $27^{+0}$  to  $29^{+6}$  weeks). Patients will be centrally assigned to one of the two treatment arms on admission through an IRT system (Interactive Response Technology, combination of voice and web response system and also referred as IVRS/IWRS).

The IRT will allocate the patient to a certain treatment group using the Pocock and Simon minimization algorithm (2) and assign the study medication kit number corresponding to the patients' treatment group. IRT specification will be fully described in a specific document, created separately.

Patients will be identified by a unique number of six digits (country in first digit, investigational site in subsequent two digits and followed by three digits with the progressive numbering of patient in each site).

For more information refer to section 6.5 of the CSP.

### 6. STATISTICAL ANALYSIS CONVENTIONS

#### 6.1 Collected Data

The study schedule is enclosed as Appendix 1.

##### 6.1.1 Disposition data

The following disposition information will be recorded and listed:

- Screen Date.
- Enrolled Date.
- Failed Date.
- Discontinued Date.
- Reason for Failure / Early withdrawal
- Completed Date.
- Parental Informed Consent Date.

Chiesi

Final 1.0

CCD-5633AA1-02

18/July/2018

---

TP-EP.BS-WW-001-05

Effective date: 29 Jul 15

Related to: SOP-EP.BS-WW-002

Page 11 of 46

## Statistical Analysis Plan

### 6.1.2 Demographic and Background Data

The following demographic and anthropometric information will be recorded and listed:

#### Neonate information

- Date/Time of Birth
- Gestational Age (Weeks)
- Gestational Age (Days)

GA in weeks will be derived using the following formula:

$$\text{GA (weeks)} + [\text{GA(Days)} / 7]$$

Derived value will be shown in the table. Both original and derived values will be listed.

- Sex
- Birth Weight (grams)
- Race ([blank], white, black or African American, Asian, American Indian or Alaska native, native Hawaiian or other pacific islander, other)
- Ethnicity ([blank], not Hispanic or Latino, Hispanic or Latino, not reported)
- APGAR score (Score Range: 1-10, [blank] possible)
- Any respiratory support in the delivery room? (Y/N)  
If yes, which method
- Chest X-Ray (CX) performed? (Y/N), performed if deemed appropriate, at screening and at Day1 24h post with
  - Date/Time performed
  - Findings (Normal/Abnormal NCS/Abnormal CS)
  - Specification of findings (if abnormal)
- Complications of Prematurity (NC) with
  - Specification of complication ([Blank], Pneumothorax, Pneumopericardium, Pneumoperitoneum, Pneumomediastinum, Apnea of prematurity AOP, Necrotizing enterocolitis NEC, Patent ductus arteriosus PDA, Pneumonia, Pulmonary interstitial emphysema PIE, Pulmonary hemorrhage, Germinal matrix/Intraventricular hemorrhage (GMH/IVH,), Cerebral parenchymal hemorrhage (CPH), Neonatal jaundice, Periventricular leukomalacia (PVL,), Retinopathy of prematurity (ROP,), Bacterial sepsis and/or meningitis, Hypoglycemia, Hyperglycemia, Hypocalcemia, Hypercalcemia, Hyponatremia, Hypernatremia, Hypokalemia, Hyperkalemia)
  - Grade of Interventricular Hemorrhage

## Statistical Analysis Plan

- Start/End Date and Time
- Ongoing (Y/N)

### Mother information

- Mother Medical/Surgical History (only entered if clinically significant) conditions with
  - Medical Disease
  - Start/End Date
  - Ongoing (Y/N)
- Mother Previous and Concomitant Medications with
  - Has the Subject's mother taken any Medication during the pregnancy or the delivery? (Y/N)
  - Trade or Generic Name
  - Start/End Date (Day, Month, Year entered separately)
  - Ongoing (Y/N)
  - Indication
- Pregnancy History (PH).
  - Type of the delivery ([blank], spontaneous, C-section with labor, C-section without labor, emergency C-section).
  - Antibiotic intake during the pregnancy (Y/N).
  - Steroid intake for fetal lung maturation (Y/N) and if yes, with information how the course was ([blank], complete, incomplete).
  - Complications (verbatim, trimester ([blank], first, second, third) and treatment given or in progress(Y/N).
  - Intrapartum complication (verbatim and treatment given (Y/N).
- Cranial Sonography (CS) with
  - Was Cranial Sonography performed? (Y/N).
  - Date/Time of sonography (Day, Month, Year entered separately).
  - Findings (Normal/Abnormal NCS/Abnormal CS).
  - Was Germinal Matrix Hemorrhage (GMH) / Intraventricular Hemorrhage (IVH) present? (Y/N) with district ([blank], right, left, bilateral) if answered YES.
  - IVH Grade ([blank] or grade 1-4 possible).
  - Was Periventricular Leukomalacia (PVL) present? (Y/N).

## Statistical Analysis Plan

- Was Cerebral Parenchymal Hemorrhage present? (Y/N).

For Cranial Sonography all values measured will be listed. Screening results will be tabulated with descriptive statistics in addition.

All medical history will be coded using Version 18.0 of the Medical Dictionary for Regulatory Activities (MedDRA).

Mother previous and concomitant medication will be coded using the World Health Organization-Drug Dictionary (WHO-DD) (Version **MAR2015**) and will be classified by Anatomical Therapeutic Chemical (ATC) categories.

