1. Signature of Parental Informed Consent can be obtained prior to birth or after birth; 2. PIP, MAP, PEEP to be monitored and collected until Day 7; 3. In a subgroup of babies when feasible; (X)⁺ Only heart rate at time 0 within 5 min from study drug administration; (X)* When applicable, at discretion of the Investigator; (X)** At least one cranial ultrasound within the first 7 days of life; (X)*** The blood sampling has to be taken with a window of 3 to 6 weeks from administration.

7.1.1 Phase 1 - On admission prior to study treatment administration (within first 24 hours of life)

The study will be explained to the parents of a potentially eligible baby prior to birth, if possible, giving the parents the maximum time to make an informed choice. Once their written informed consent has been obtained either prior to or after birth, the neonate's eligibility to take part in the study will be assessed according to the post-birth inclusion and exclusion criteria. If the baby becomes eligible, then the medical history of the mother, the complications during pregnancy and the prenatal use of corticosteroids will be collected.

If the baby becomes eligible, then the following information will be collected:

- birth weight;
- Apgar score;
- neonatal complications and concomitant medications;
- clinical signs of RDS (Chest X-ray when applicable, at discretion of the Investigator);
- SpO₂ along with vital signs (systolic and diastolic blood pressure, heart rate);
- Respiratory support (invasive or non-invasive), ventilatory settings (PIP, FiO₂, PEEP, MAP), OSI and RSS;
- Invasive oxygen measurements (A-a oxygen gradient, OI), when feasible, in a subgroup of infants
- 400 µL blood sample for immunogenicity assessments in serum ;
- Cranial ultrasound when applicable, at discretion of the Investigator;
- Tracheal aspirates for the evaluation of inflammatory biomarkers to be shipped to a central laboratory for analysis, when feasible, in a subgroup of patients;
- Any adverse events occurring after the Informed Consent Form Signature, in the AE Form of the eCRF. If the abnormality starts prior to the study drug administration and it is listed among the Morbidities or Complications of Prematurity (see Section 10.8) which are clinically expected outcomes in preterm neonates aged between 24⁺⁰ and 29⁺⁶ weeks, it should be recorded in the dedicated form.

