7.1.2 Phase 2 - Up to 24 hours after test treatment administration

Once the neonate's eligibility to take part in the study is confirmed, the Investigator will have to call/check the IRT to receive the kit number to be used and then the test treatment will be administered within 24 hours from birth. The tear-off sticker from the medication box will be applied in the appropriate section of the surfactant accountability log.

At the administration (Time 0) the following information will be collected:

- SpO₂ and heart rate within 5 min from study drug administration;

Then, after the administration, the following information will be collected:

- SpO₂ and vital signs (systolic and diastolic blood pressure, heart rate) at 30 min, 1 hour, 3, 6, 12, 18 and 24 hours after test treatment administration;
- ventilator settings (PIP, FiO₂, PEEP, MAP), RSS and OSI at 30 min, 1 hour, 3, 6, 12, 18 and 24 hours after test treatment administration. Mechanical ventilation will be monitored and any change in invasive and non-invasive ventilation will be recorded with its date and time;
- Invasive oxygen measurements (A-a oxygen gradient, OI), when feasible, in a subgroup of infants at 3, 6, 12, 18 and 24 hours after treatment;
- Use of oxygen alone (supplemental oxygen without invasive or non-invasive ventilator support) will be monitored and any occurrence will be recorded with its date and time of start and end;
- Blood tests within 24 hours after test treatment administration, defined as full blood count (FBC), urea, creatinine and electrolytes (sodium, potassium, calcium, phosphorus), alanine aminotransferase (ALT), aspartate aminotransferase (AST), glucose, C-reactive protein;
- RDS or other respiratory anomalies 's diagnosis confirmation (Chest X-ray when applicable, at discretion of the Investigator);
- At least one cranial ultrasound within the first 7 days of life;
- Tracheal aspirates for the evaluation of inflammatory biomarkers to be shipped to a central laboratory for analysis, when feasible, in a subgroup of patients;
- new neonatal concomitant medications and adverse events as well as changes in those already reported.

In the event that multiple measurements are available, the measurements closest to the required time point are to be collected.

7.1.3 Phase 3 - 2 days after test treatment administration (from 24hrs ^{+ 1min} to 48hrs after dosing)

The following information will be collected:

- SpO₂

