12.3.5 Safety variables

Adverse Events

Incidence of AEs, related AEs (ADRs), serious AEs and AEs leading to death will be summarized by treatment group both in term of frequency of neonates with at least one AE and in term of frequency of AEs (number of events). All the aforementioned categories of AEs will be summarized by System organ Class (SOC) and Preferred Term (PT).

Major neonatal morbidities (see section 10.8) will be summarized separately by treatment group in term of frequency of neonates with at least one complication and in term of number of complications.

Vital Signs and SpO2

At each time point (at 0 -for HR only-, 30 minutes, at 1, 3, 6, 12, 18, 24 hours, Days 2, 3, 5, 7 and 28 PNA, discharge home and at 36 weeks PMA), the absolute value and the change from baseline in vital signs (SBP, DBP and HR) will be summarized by treatment group using descriptive statistics.

SpO2 during administration (time 0) will be summarized as well.

Time curve of the mean change from baseline in the first week of life will be presented by treatment group.

Laboratory data

Hematology and chemistry parameters will be listed together with their normal ranges when available.

Immunogenicity data

The levels of antibodies in serum will be listed.

Bayley Scales

Bayley Scales of Infant Development measured at 24 months (± 3 months) corrected age will be summarized by treatment by means of descriptive statistics.

Health status questionnaire

Health status questionnaire (health problems, illnesses, injuries, well-being, diet, respiratory assessment) assessed at 24 months (± 3 months) corrected age will be summarized by treatment by means of descriptive statistics.

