#### DISPOSITION AND DEMOGRAPHIC DATA

Table 14.1.1.1 Patient Disposition (All Screened)

\*Table 14.1.1.2 Patient Disposition:(All Randomized )

Table 14.1.1.5 Major Protocol Deviations (ITT population)

Table 14.1.1.6 Minor Protocol Deviations (ITT population)

\*Table 14.1.1.7 Summary of Analysis Sets (All Randomized)

\*Table 14.1.2.1 Demographic Characteristics (ITT Population)

\*Table 14.1.2.2 Demographic Characteristics (Safety Population)

Table 14.1.4.1 Chest x-Ray (Safety Population)

Table 14.1.4.2 Complications of Prematurity at Baseline (Safety Population)

Table 14.1.5.1 Mother Medical and Surgical History (Safety Population)

Table 14.1.5.2 Pregnancy History (Safety Population)

Table 14.1.6.1 Mother Previous and Concomitant Medication (Safety Population)

Table 14.1.6.2 Neonatal Concomitant Medication (Safety Population)

Table 14.1.7.1 Cranial Sonography at Screening (Safety Population)

\*Table 14.1.8.1 Treatment Exposure (Safety Population)

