#### **DEMOGRAPHICS AND OTHER BASELINE CHARACTERISTICS**

Listing 16.2.4.1 Demographic Characteristics (All Randomized)

Listing 16.2.4.2 Complications of Prematurity (All Randomized)

Listing 16.2.4.3 Chest X-Ray (All Randomized)

Listing 16.2.4.4 Cranial Sonography (All Randomized)

Listing 16.2.4.5.1 Mother Medical and Surgical History (All Randomized)

Listing 16.2.4.5.2 Pregnancy History (All Randomized)

Listing 16.2.4.6.1 Mother Previous and Concomitant Medication (All Randomized)

Chiesi

Final 1.0

CCD-5633AA1-02

18/July/2018

---

TP-EP.BS-WW-001-05

Effective date: 29 Jul 15

Related to: SOP-EP.BS-WW-002

Page 42 of 46

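### Only the discretionary pre-dose cranial scan is tabulated; no specified table gives post-dose IVH grade by arm, so grade 3-4 haemorrhage cannot be separated from grade 1-2

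*SAP*

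**What the plan says.** **Collection.** SAP 6.1.2 (Cranial Sonography, under Mother information) records for each scan whether haemorrhage is present and its grade, "IVH Grade ([blank] or grade 1-4 possible"), together with PVL and cerebral parenchymal haemorrhage as yes/no items.

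**Timing.** Before dosing, Protocol 7.1.1 asks for "Cranial ultrasound when applicable, at discretion of the Investigator". Under the post-dose phases (Protocol 7.1.2 to 7.1.6) it asks for "At least one cranial ultrasound within the first 7 days of life".

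**Output from the scans.** SAP 6.1.2 states: "For Cranial Sonography all values measured will be listed. Screening results will be tabulated with descriptive statistics in addition". The table list in SAP section 8 agrees. Its only sonography entry is "Table 14.1.7.1 Cranial Sonography at Screening (Safety Population"). The complete scan data appear as "Listing 16.2.4.4 Cranial Sonography (All Randomized").

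**Output from adverse events.** Protocol 10.8 names germinal matrix/intraventricular haemorrhage, cerebral parenchymal haemorrhage and PVL as complications of prematurity. It requires their onset or worsening after dosing to be reported as an adverse event. Protocol 12.3.5 adds: "Major neonatal morbidities (see section 10.8) will be summarized separately by treatment group in term of frequency of neonates with at least one complication", as well as the number of complications. SAP section 8 plans Table 14.3.1.3.2 (treatment-emergent events by system organ class and preferred term), Table 14.3.1.3.4 (serious events, same layout) and Table 14.3.1.3.5 (neonatal morbidities).

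**Objective.** The mid-term efficacy objective in SAP 1.1 ends with "other major co-morbidities of prematurity".

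**The concern.** The tabulated scan is the one treatment cannot have influenced. The scans taken after dosing, with their grades, are left for the reader to count from a listing.

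Severity is what matters when brain haemorrhage is compared between two surfactants. If one arm had the same number of babies with IVH but more of them at grade 3 or 4, an ungraded count would show no difference. Protocol section 1 says the trial is to inform whether development continues, so a shift of that kind should be visible in the report. Severe IVH also falls under a main objective, and the other mid-term items in that objective receive a between-arm estimate.

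**Working it through.** The plan states no figure to reproduce. Protocol 12.1 says that no power calculation was done. The check is therefore a trace of where each finding goes, followed by an illustration on assumed rates.

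**Step 1. Trace the outputs.**

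| Data | By-arm table | IVH grade shown? |
|---|---|---|
| Pre-dose scan | 14.1.7.1 | Possible, but pre-dose |
| Post-dose scans | None (Listing 16.2.4.4 only) | In the listing only |
| Post-dose IVH, PVL, parenchymal haemorrhage as adverse events | 14.3.1.3.2, 14.3.1.3.5, and 14.3.1.3.4 if serious | Not specified |

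Tables built from post-dose scans: 0. Tables specified by post-dose IVH grade: 0. By-arm tables that carry these lesions as ungraded events: at least 2.

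**Step 2. Can grade be recovered from the adverse event tables?** Protocol 10.3 rates events as mild, moderate or severe, which is not an IVH grade. SAP 6.3.11.1 plans no breakdown by intensity in any case. SAP 6.1.2 does include an IVH grade on the complications-of-prematurity form, but Protocol 10.8 uses that form for conditions that began before dosing. In SAP 6.1.3.1.3, IVH is a single term without grade. SAP 6.3.11 has no methods text for Table 14.3.1.3.5, so nothing commits it to a grade split.

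**Step 3. Compare with the rest of the objective.** SAP 6.3.12.1.7 gives BPD, mortality/BPD, mortality and RDS-associated mortality a Cochran-Mantel-Haenszel comparison by gestational age group, with relative risk and 95% CI. The co-morbidities get counts only.

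**Step 4. What an ungraded row can hide (all event counts assumed).** Take n = 63 per arm (SAP section 4) and 22 babies with any IVH in each arm.

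- Arm 1: 6 at grade 3-4, so 22 − 6 = 16 at grade 1-2. 6/63 = 9.5%.
- Arm 2: 13 at grade 3-4, so 22 − 13 = 9 at grade 1-2. 13/63 = 20.6%.
- Ungraded row: 22 versus 22.
- Grade 3-4 difference: 7/63 = 11.1 points.
- Standard error: √(0.0952 × 0.9048/63 + 0.2063 × 0.7937/63) = √(0.001368 + 0.002599) = 0.0630.
- 95% CI: 11.1 ± 1.96 × 6.30 = −1.2 to 23.5 points.

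**Step 5. Precision the added table could offer.** For a common rate p, the 95% half-width is 1.96 × √(2p(1 − p)/63). Power is for a doubling of p at two-sided 5%. The documents give no rate for severe IVH or PVL, so a range is shown.

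| Assumed p | Half-width (points) | Power for a doubling |
|---|---|---|
| 5% | 7.6 | 18% |
| 10% | 10.5 | 35% |
| 15% | 12.5 | 52% |
| 20% | 14.0 | 69% |

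These use all 63 babies per arm. Fewer babies scanned after dosing would widen the intervals.

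**The case against.** A reader might infer from the scan rule that severe brain injury is never compared between the arms, or that an excess of PVL would appear in no table. The documents do not support either reading. Protocol 10.8 makes post-dose IVH, PVL and parenchymal haemorrhage reportable as adverse events. They then appear by arm in Tables 14.3.1.3.2 and 14.3.1.3.5, and in 14.3.1.3.4 when serious. PVL and parenchymal haemorrhage each have their own term. Appendix IV of the protocol describes the latter as a lesion extending into brain tissue in association with IVH, so bleeding with that extension is partly visible. What remains hidden is the grade itself.

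SAP 6.3.1 also says in general terms that all parameters will be summarised, and that descriptive statistics will be by treatment. That might be read to cover the post-dose scans. The specific rule in 6.1.2 and the table list both limit tabulation to screening, and a programmer would follow those.

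The layout of Table 14.3.1.3.5 is not given, so it could turn out to include a grade split. This is fair, and it is why the point concerns what is specified. The same gap means that the Protocol 12.3.5 wording on babies with at least one complication may be read as a pooled count or as a count per complication. Nothing here depends on which.

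Finally, the trial is exploratory, the morbidities are safety variables summarised descriptively, and there is no multiplicity plan. An independent board reviews serious events, and Bayley scores follow at 24 months under a separate SAP. This is a sound argument against requiring estimates for all 21 items in Protocol 10.8 (13 conditions and 8 laboratory abnormalities). It does not answer the missing grade, since neither the board nor the later assessment produces that table in the trial report.

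**Conclusion.** The point holds in a limited form. Post-dose brain lesions are shown by arm as ungraded, adverse-event-reported counts. No specified table gives post-dose IVH grade, so grade 3-4 cannot be separated from grade 1-2 by arm. No effect estimate is planned, although major co-morbidities are part of a main objective. Meanwhile the scan that does get a table is optional and precedes treatment.

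The trace through the documents rests on no assumption. The 6 versus 13 example and the interval widths rest on assumed rates. They show what could be missed and how imprecise an estimate would be; they do not predict a result. With 63 per arm, a doubling from an assumed 10% would be detected about 35% of the time, so the added table would display a signal and could not settle one.

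On timing, the required scan is defined by days of life, while its placement under the post-dose phases suggests that a scan after dosing was meant. The wording and the placement should be reconciled.

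The change is worth making: it uses data already collected and affects what the report can say about severe brain injury.

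**What to change.** In SAP 6.1.2, SAP 6.3.11 and the section 8 table list, add one by-arm table in the Safety population, built from the ultrasound data, with:

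- worst post-dose IVH grade in three categories (none, 1-2, 3-4), PVL, and cerebral parenchymal haemorrhage;
- the number of babies scanned after dosing as the denominator;
- a flag for findings already present before dosing;
- for grade 3-4 IVH and for PVL, a risk difference, or a relative risk stratified by gestational age group as in SAP 6.3.12.1.7, with 95% CI, labelled descriptive.

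Separately, reconcile the wording of the first-week scan requirement with its placement under the post-dose phases.

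The cost is one extra table and a short methods paragraph, with no new data collection for the table. The intervals will be wide and there is no multiplicity control, so the table should say so. If the database is already locked, the SAP's own introduction provides for additional analyses in an addendum.
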